# 9.6 Day $28 \pm 2$ days

Participants will complete the following assessments and return unused investigational product, completed study diaries and modified WURSS-24 Questionnaires. Participants will be fasted (≥ 8 hours).

#### Assessments include:

- 1. Return and review study diaries and modified WURSS-24 Questionnaires
- 2. Return unused investigational product in the original packaging and remnants and calculate compliance by counting the returned unused investigational product
- 3. Review concomitant therapies and adverse events
- 4. Seated BP and HR measurements
- 5. Collection of blood samples for the analysis of:
  - a. CBC, electrolytes (Na, K, Cl), glucose, eGFR, creatinine, AST, ALT, ALP, and total bilirubin
  - b. ESR, CRP, complement C3, complement C4, IgG, IgM, IgA, CD3+, CD8+, CD4+, CD45+, TCR $\gamma\delta$ +, CD3-CD16+CD56+
  - c. Cytokines, HMGB1, NF-κB, Nrf-2, 8-iso-prostaglandin F2α, CAT, GSH-Px, SOD, MDA, AGEs, HI titers for specific strains of virus for future analysis
- 6. Administer Vitality Questionnaire (Section 9.9.4)
- 7. Administer COVID-19 QoL (Section 9.9.5)
- 8. Administer flu vaccine (QIV)
- 9. Dispense new IP
- 10. Dispense new study diaries
- 11. Dispense new modified WURSS-24 Questionnaires (Section 9.9.3)

The next appointment will be scheduled for Day  $56 \pm 2$  days.

Participants will be reminded to follow all instructions provided prior to their next appointment.

## 9.7 Processing Participants who get COVID-19 or Flu After Vaccination and Prior to Day 56

The WURSS-24 Questionnaires and daily diaries will be reviewed by clinic staff. Clinic staff will identify those participants that self-report they have COVID-19 or flu. Regarding flu, participants will be queried on if they have a diagnosis from their PCP. In the absence of such a diagnosis, based on indicated symptoms, participants will be assessed on a case-by-case basis by the QI.

Participants with self-reported diagnosis COVID-19 will be removed from the study. A COVID-19 diagnosis will be considered an AE and AE follow-up procedures will be followed.

#### 9.8 Day $56 \pm 2$ days

Participants will complete the following assessments and return unused investigational product, completed study diaries and modified WURSS-24 Questionnaires. Participants will be fasted (≥ 8 hours).

#### Assessments include:

1. Return and review study diaries and modified WURSS-24 Questionnaires

- 2. Return unused investigational product in the original packaging and remnants and calculate compliance by counting the returned unused investigational product
- 3. Review concomitant therapies and adverse events
- 4. Urine pregnancy test for female potential participants that are of child-bearing potential
- 5. Seated resting BP and HR measurements
- 6. Weight measurement
- 7. Collection of blood samples for the analysis of:
  - a. CBC, electrolytes (Na, K, Cl), glucose, eGFR, creatinine, AST, ALT, ALP, and total bilirubin
  - b. ESR, CRP, complement C3, complement C4, IgG, IgM, IgA, CD3+, CD8+, CD4+, CD45+, TCR $\gamma\delta$ +, CD3-CD16+CD56+
  - c. Cytokines, HMGB1, NF-κB, Nrf-2, 8-iso-prostaglandin F2α, CAT, GSH-Px, SOD, MDA, AGEs, HI titers for specific strains of virus for future analysis
- 8. Administer Vitality Questionnaire (Section 9.9.4)
- 9. Administer COVID-19 QoL (Section 9.9.5)

#### 9.9 Clinical Assessments and Procedures

Calculations or measurements of specific parameters are required, as indicated in the Schedule of Assessments. Instructions for determining these parameters are provided in the following sections.

# 9.9.1 Height and Weight

Weight measurements will be performed with shoes removed and bladder empty on calibrated scales for all measurements.

At least two separate measurements will be taken. If the two measurements are more than 0.5 kg (1.1 lbs) apart, a third measurement will be taken. The two closest values will be selected for computation. Measurement of height will be performed with the participant's shoes removed. The participant's knees will be straightened, and head held upright.

#### 9.9.2 Blood Pressure and Heart Rate

Seated, resting blood pressure assessment:

The participant should be seated comfortably with their back supported and the upper arm bared without restrictive clothing. Feet should be flat on the floor and legs will not be crossed. The participant will rest in this position for at least five minutes prior to the first reading.

#### At baseline:

Seated blood pressure will be checked in both arms to ensure that the arm with the higher blood pressure reading will be used for BP measurements of the study. The arm chosen for use at the initial visit will be documented in the study file and used in all subsequent visits. Participant should be queried about their usual blood pressure. As per the QI's opinion, a high office blood pressure should be rechecked after the participant is given a glass of water and is rested for 15 minutes.

At subsequent study appointments:

Once enrolled in the study, BP will be measured in the chosen arm. Two readings will be made, and if there is questionable disparity a third reading will be taken.

Heart Rate (beats/min) will be measured simultaneously during blood pressure recording.

#### 9.9.3 Modified WURSS-24 Questionnaire

The WURSS is a questionnaire used to evaluate the negative impact of acute URTIs. The WURSS-24 contains 24 items scored on a Likert-type severity scale. It contains the same items as the WURSS-21 along with headache, body ache, and fever to capture influenza-like illness symptoms (32, 33). The modified WURSS-24 used in this study include a revision that refer to "symptoms" rather than "cold" to clarify that symptoms may be due to any URTI not specific to cold. A new URTI episode is defined as the sudden appearance of 1 or more symptoms captured by questions 2 to 5 of the WURSS-24 Questionnaire, not attributed to allergies (as reported by participants) with at least 2 prior days of 'not sick' as defined by Murdoch et al. (32). The WURSS-24 Questionnaire was used to capture the incidence, frequency and severity of URTI symptoms and has been validated by Barrett et al. (34).

#### 9.9.4 Vitality and Quality of Life Questionnaire

The Vitality and QoL Questionnaire will be used to assess the energy levels and quality of life of the participants. The 31-item questionnaire consists of a 7-point Likert scale, with answers ranging from 1 to 7. The higher the summative score the more vitality that was subjectively perceived by the participants.

# 9.9.5 COVID-19 Impact on Quality of Life (QoL) Questionnaire

The impact of the COVID-19 pandemic on the wellbeing of participants will be assessed using the COVID-19-Impact on Quality of Life (COV19-QoL) scale v1.5 (35). This 6-item questionnaire consists of a 5-point Likert scale to assess the impact of COVID-19 on QoL. The higher the score, the greater impact on quality of life and related domains subjectively perceived by participants.

#### 9.9.6 Blood Sample Collection

An appropriately trained and qualified personnel will perform the venipuncture procedure to collect the necessary blood samples as per standard phlebotomy techniques.

#### 9.9.7 Compliance

Compliance will be assessed by counting the returned unused study product. Compliance is calculated by determining the number of dosage units taken divided by the number of dosage units expected to have been taken multiplied by 100.

$$\frac{number\ of\ dosage\ units\ taken}{number\ of\ dosage\ units\ expected\ to\ have\ been\ taken}\times 100\%$$

In the event of discrepancy between the information in the study diary and the amount of study product returned, use will be based on the product returned unless an explanation for loss of product has been provided. Participants found to have a compliance of <80% or >120% will be counseled.

# 9.10 Laboratory Analyses

Blood samples will be drawn from the participants at screening, baseline (Day 0), Day 28, and at the end of the study (Day 56) as indicated in the Schedule of Assessments.

Protocol 21UIHU A randomized, triple-blind, placebo-controlled, parallel clinical trial to investigate two products on supporting immune function in healthy adults

Protection of participant confidentiality will extend to all data generated from the assaying of these samples. These samples will be alphanumerically coded and the persons performing the analysis will not be aware of the participant's identity or the product they received.

The total blood volume collection for the laboratory assessments listed above will be approximately 183 mL, over the period from screening to end of study 56 days. At any study visit, blood loss per volunteer is not expected to exceed 58 mL. Additional blood samples may be collected during the study in order to perform or repeat laboratory tests outlined in the Schedule of Assessments if needed.

A central laboratory will be used in this study to measure blood parameters.

Urine pregnancy test will be performed.

### 9.11 Termination of the Study

In the case of premature termination of the Study, participating investigators/participants, and the Institutional Review Board must be promptly informed of the termination. In the event of early termination, as many assessments will be completed as agreed upon by participant.

#### 9.12 Protocol Amendments

If amendments to the study protocol are required after approval such changes will be captured in writing, the reasons for the change documented, and signed and dated by the Sponsor. Any such amendments may be subject to IRB and Health Canada review/approval prior to implementation. Exception: if it becomes necessary to alter the protocol to eliminate an immediate hazard to participants, an amendment may be implemented prior to IRB approval. In this circumstance, the Qualified Investigator must notify IRB and Health Canada in writing within five (5) working days of the implementation.

#### 10 SAFETY INSTRUCTIONS AND GUIDANCE

## 10.1 Adverse Events and Laboratory Abnormalities

#### 10.1.1 Adverse Events

An AE is any untoward medical occurrence in a clinical investigation participant who has been administered an investigational product and does not necessarily have a causal relationship with this investigational product. An AE can be any unfavorable and unintended sign (including an abnormal laboratory finding), symptom, or disease temporally associated with the use of a product, whether or not it is considered related to that product. Pre-existing conditions that worsen during a study are to be reported as AEs. In this study, symptoms associated with URTIs that are listed on the WURSS-24 Questionnaire will not be classified as an AE. Further, AEs due to the influenza vaccine rather than the investigational product will be assessed and documented.

During the study, participants should record any adverse effects in their diary. At each visit the participant will be asked, "Have you experienced any difficulties or problems since I saw you last?". Any AEs will be documented in the study record and will be classified according to the description, duration, intensity, frequency, and outcome. The QI will assess any AEs and decide causality.

Intensity of AEs will be graded on a three-point scale (mild, moderate, severe) and reported in detail in the study record:

Mild: Awareness of event but easily tolerated

Moderate: Discomfort enough to cause some interference with usual activity

Severe: Inability to carry out usual activity

The causality relationship of investigational product to the adverse event will be assessed by the Qualified Investigator as either:

Most probable: There is a reasonable relationship between the investigational product and AEs. The

event responds to withdrawal of investigational product (dechallenge) and recurs with

rechallenge when clinically feasible.

Probable: There is a reasonable relationship between the investigational product and AEs. The

event responds to dechallenge.

Possible: There is a reasonable relationship between the investigational product and AEs.

Dechallenge information is lacking or unclear.

Unlikely: There is a temporal relationship to the investigational product administration but there

is no reasonable causal relationship between the investigational product and the AEs.

Not related: There is no temporal relationship to investigational product administration or there is a

reasonable causal relationship between non-investigational product, concurrent disease,

or circumstance and the AEs.

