It is well established that various nutrients including vitamin A, B12, folate, selenium, iron, copper and omeg-3 fatty acids play an important role in supporting the immune system and optimal nutritional status is key in protection against viral infections (14). Further, the addition of adjuvant supplements or nutritional

A randomized, triple-blind, placebo-controlled, parallel clinical trial to investigate two products on supporting immune function in healthy adults

interventions have been investigated to improve the immune response to influenza and efficacy of the influenza vaccine (15-18). A vaccine model is used to examine if prophylactic supplementation modulates the immune response that is induced by the immunological challenge of administering the vaccine (17, 19).

To examine the role of dietary supplements in supporting immune function in response to influenza vaccination using this vaccine model, there are two investigational products (IPs) being used in the current study. One product, UP360, includes ingredients *aloe vera* gel powder, rosemary and *Poria cocos* extracts and the other, UP446, contains *Acacia catechu* (*Senegalia catechu*) and *Scutellaria baicalensis*. Through distinct mechanisms of action, these ingredients have been shown to activate the immune system, reduce inflammation and oxidative stress and protect against lung damage.

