#### 10.3 Reporting of SAEs And Unexpected Adverse Reactions

The Qualified Investigator will be responsible for classification of an AE as an SAE within 24 hours of notification. Causality should be signed off by the Qualified Investigator prior to reporting to ethics and regulatory bodies. Notification of any serious adverse events must be made in writing to the study Sponsor. The IRB will be notified of all product related SAEs and unexpected adverse reactions. All blinded SAE's or unblinded-participant-on-active product SAE's will be reported to the Therapeutics Products Directorate (TPD) in an expedited manner.

KGK Science Inc. must notify the TPD of all blinded or unblinded-participant-on-active product serious adverse events and reactions as follows:

If it is neither fatal or life threatening, within 15 calendar days after the day on which the Sponsor becomes aware of the information; and

If it is fatal or life threatening, must be reported as soon as possible, but not later than seven (7) days after the day on which the Sponsor becomes aware of the information.

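### The causality scale lets one post-vaccination event be both *Possible* and *Not related*, and has no place for a joint product and vaccine cause

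*Protocol*

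**What the plan says.** Protocol section 10.1.1 gives a five-level causality scale and leaves the rating to the Qualified Investigator: "The QI will assess any AEs and decide causality". Three points matter.

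- The lowest level has two limbs joined by *or*. It opens "Not related: There is no temporal relationship to investigational product administration or there is a" and continues "reasonable causal relationship between non-investigational product, concurrent disease", or circumstance, and the event. Either limb is enough.
- The lowest level that accepts a product link reads "Possible: There is a reasonable relationship between the investigational product and AEs", with dechallenge information lacking or unclear. It does not ask that other causes be excluded.
- The vaccine is presented as an alternative to the product: "Further, AEs due to the influenza vaccine rather than the investigational product will be assessed and documented".

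Section 4 states that "there are two investigational products (IPs) being used in the current study" and names UP360 and UP446, so the influenza vaccine (QIV) falls outside the term. The same section gives the purpose of the vaccine model, which is to "examine if prophylactic supplementation modulates the immune response that is induced by the immunological challenge of administering the vaccine".

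Sections 6, 8.6 and 8.9 put the vaccine in all three arms on Day 28 of a 56-day dosing period. On reporting, section 10.3 says "The IRB will be notified of all product related SAEs and unexpected adverse reactions". Section 11.3.2 plans a frequency table by category and arm, and separately reports causality for each event.

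**The concern.** A causality scale should place each event in one category. This one does not do so for the events most expected after Day 28. A vaccine reaction has an obvious alternative cause, which satisfies the second limb of *Not related*. If the investigator also thinks the product may have contributed, *Possible* is satisfied too. Two careful assessors could code the same event at different levels and both be following the text.

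This trial is exposed because vaccine and product are given together by design and the question is whether one changes the response to the other. A changed reaction to the vaccine is therefore a foreseeable joint effect, and the scale offers only one cause or the other. At stake are the per-event causality report and whether an SAE is notified to the IRB as product related.

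**Working it through.** The main check is textual; the protocol gives no figure on this point to reproduce.

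**1. The five definitions side by side (section 10.1.1)**

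| Category | Link to the product | Dechallenge | Other cause |
|---|---|---|---|
| Most probable | reasonable | responds, and recurs on rechallenge where feasible | not mentioned |
| Probable | reasonable | responds | not mentioned |
| Possible | reasonable | lacking or unclear | not mentioned |
| Unlikely | temporal, but no reasonable causal link | – | not mentioned |
| Not related | no temporal link, **or** the next column | – | reasonable cause outside the product: sufficient alone |

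**2. A test event.** Take an injection-site reaction in the days after vaccination, in a participant for whom the investigator finds a product contribution reasonable.

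- *Temporal link to product:* yes. Dosing runs 56 days from Day 0 and vaccination is on Day 28, so 56 − 28 = 28 days of dosing follow it, half the period (visit windows of ±2 days aside).
- *Reasonable vaccine cause:* yes. Section 13.3 lists such reactions among the vaccine's risks.
- *Possible:* met if dechallenge is unclear. This will be common, because a reaction to a single injection would ordinarily settle whether or not the product is stopped.
- *Unlikely:* not met, because a reasonable product link exists.
- *Not related:* met through its second limb.

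The event therefore fails the weaker denial (*Unlikely*) and satisfies the stronger one (*Not related*). The scale is out of order at its lower end, and nothing in section 10.1.1 sets precedence.

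**3. What depends on the coding**

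| Output | Depends on causality? | Section |
|---|---|---|
| AE frequency table by category and arm | No | 11.3.2 |
| Causality reported for each AE | Yes | 11.3.2 |
| Written SAE notice to the Sponsor | No | 10.3 |
| Regulator (TPD) reporting of blinded SAEs | No condition stated | 10.3 |
| IRB notice of product-related SAEs | Yes | 10.3 |

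**4. Who is exposed.** Participants who reach Day 28. The ceiling is 75 (25 per arm). If the 20% loss allowed for in section 11.1 all fell before vaccination, the number would be 75 × 0.80 = 60 (20 per arm).

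**5. Side check: how well would the arm comparison reveal a joint effect?** The protocol gives no reaction rates, so placebo rates of 20%, 30% and 40% are assumed. For two proportions at two-sided 5%, with p̄ the mean of p₁ and p₀:

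power = Φ{ [ (p₁ − p₀) − 1.96·√(2p̄(1 − p̄)/n) ] / √[ (p₁(1 − p₁) + p₀(1 − p₀))/n ] }

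With n = 25, p₀ = 0.20 and p₁ = 0.40: (0.20 − 1.96 × 0.1296)/0.1265 = −0.427, giving 33.5%. Across the three assumed rates:

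| Excess over placebo | n = 25 per arm | n = 20 per arm |
|---|---|---|
| 10 points | 11–13% | 9–11% |
| 20 points | 29–34% | 24–28% |
| 30 points | 57–61% | 48–51% |

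The by-arm table keeps these events in view but would often not distinguish a moderate excess, so the individual ratings carry some weight.

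**The case against.** A reader might infer that the scale forces every event with a plausible vaccine cause into *Not related*, so that product-enhanced reactions are removed by definition. The protocol does not support that. The three product-positive categories do not require the vaccine to be ruled out, and the Qualified Investigator decides. The text permits *Not related*; it does not compel it.

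A reader might also infer that a product-by-vaccine reaction would go unseen. That does not follow either. The placebo arm is vaccinated, and adverse events are tabulated by arm whatever their causality. SAEs go to the Sponsor, and blinded SAEs to the regulator, with no causality condition in those sentences. The IRB sentence also names unexpected adverse reactions. The low power in the side check comes from the size of the arms, and recoding causality would not change it.

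Two further limits stand. Section 4 speaks of modulating the response and describes anti-inflammatory as well as immune-activating properties, so the protocol does not predict worse vaccine reactions. And section 10.1.1 excludes from adverse events the URTI symptoms listed on the WURSS-24. That list includes tiredness, headache and body aches, which resemble several vaccine reactions, so some may never reach the causality scale.

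Whether to tabulate events separately before and after vaccination is a choice that can be left to a statistical analysis plan, and is not part of this point.

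What the objection leaves untouched is the definition itself: the categories overlap, their order is inconsistent, and joint causation has no category.

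**Conclusion.** The point holds as a defect in a stated definition. For events after the Day 28 vaccination, *Possible* and *Not related* are not mutually exclusive, *Not related* is easier to satisfy than *Unlikely*, and no wording covers a joint cause. The practical reach is narrow: the causality reported for each event, and the IRB notice of product-related SAEs. Arm-level counts and the other two SAE routes are unaffected.

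The conclusion rests on reading the vaccine as a non-investigational product, which follows from section 4 and from the contrast drawn in section 10.1.1. It does not depend on the assumed reaction rates in the side check, nor on any prediction of how the investigator will code. It is worth correcting because the trial deliberately combines the two exposures and the correction is cheap.

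**What to change.** 1. In section 10.1.1, amend *Not related* so that a cause outside the product is not sufficient alone: the definition should also require that there is no reasonable causal relationship to the investigational product.
2. Rate relatedness to the investigational product and to the QIV as two separate items, and allow both to be positive. Reword the sentence that sets vaccine against product to match.
3. In section 10.3, state that an SAE with a reasonable product contribution counts as product related for the IRB notice even when the vaccine is also a cause.

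The cost is a few sentences of text and one extra field on the adverse event form. The downside is that somewhat more events will be labelled possibly product-related.

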#### 10.1.2 Serious Adverse Event

An SAE is any experience that suggests a significant hazard, contraindication, side effect or precaution. It is any AE that results in any of the following outcomes:

- 1. Death
- 2. A life-threatening adverse event
- 3. Inpatient hospitalization or prolongation of existing hospitalization
- 4. A persistent or significant disability or incapacity
- 5. A congenital anomaly/birth defect in the offspring of a participant who received the study investigational product

Important medical events that may not be immediately life-threatening or result in death or hospitalization but may jeopardize the participant or may require intervention to prevent one of the outcomes listed above. Examples of such events are intensive treatment in an emergency room or at home for allergic bronchospasm; blood dyscrasias or convulsions that do not result in hospitalization; or the development of drug dependency or drug abuse.

